The primary objective is to evaluate the number of treatments required within the allocated ten treatments to effect improvement in pain in both groups. Pain resolution will be assessed using the 0-10 Numeric Pain Rating Scale (0-10 NPRS). NPRS will be given at baseline, the fourth, the eighth and the tenth treatment or earlier if resolution of symptoms occurred without the requirement of the allocated ten treatments. The secondary objective is to compare the outcomes between the treatment arms for dyspareunia, bladder and musculoskeletal pain, and some menstrual cycle related pain symptoms with the Female Sexual Function Index questionnaire and an abbreviated version of the International Pelvic Pain Questionnaire (IPPQ). These questionnaires will be completed at pre-treatment and at the final session. The Pain Treatment Satisfaction Scale questionnaire (PTSS) measures the treatment satisfaction in both groups which will be provided only at the final treatment.

Clinical Research Ethics Committee of the Cork Teaching Hospitals.

Table 1: Inclusion and exclusion criteria for recruitment

Inclusion criteria

- Females with non-cyclical CPP including dyspareunia and associated pelvic floor pain-related dysfunctions such as bladder pain, pain with urination or dyschezia.
- They should present with palpable high pelvic floor muscle tone and tenderness on vaginal examination in a clinical setting with a pain score of >4/10.
- They can present with lower abdominal pain, pelvic pain and/or groin pain and pain on sitting.
- Pain worsened with pelvic floor stretching activities like insertion of tampon or intercourse (27).
- Visceral conditions like interstitial cystitis are difficult to exclude at gynaecology review, as they can mimic CPP symptoms (1).
- Smokers are included.
- Nulliparous and parous women included.
- Age 18 to 60 years

Exclusion criteria

- Body mass index greater than 30, as the required needle length is not available.
- Chronic back pain of over 6 month duration and under pain management team.
- Orthopaedic back surgeries with implants.
- Pelvic pathologies like endometriosis, fibroids, cysts and polycystic ovarian syndrome.
- Pregnancy related pelvic girdle pain.
- Pregnant during the trial.
- Pelvic organ carcinomas.
- Undergoing cancer treatment.
- After gynaecology surgery of less than 16 weeks.
- After cardiovascular, gastroenterology, renal or orthopaedic surgery of less than 6 month's postoperative.

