 Group A: 1st treatment – Trial checklist to be completed by the physiotherapist. Consent forms to be filled by the participants. Complete three baseline questionnaires (NPRS, FSFI, IPPQ). Subjective and objective assessment along with education of muscle involvement and treatment entailed. Education on good bladder, bowel and dietary habits if indicated. Signing of consent forms for treatment and the trial. Assess and treat with TPR and distention for the PFM, pelvic and abdominal muscles as per presentation. 4th treatment – complete NPRS 8th treatment or when ceasing treatments due to positive outcomes – to complete four final questionnaires (NPRS, FSFI, IPPQ, PTSS). 10th treatments – if no resolution is achieved, 	Initial assessment of posture, spine and the PFM. Treatment is for 30-45 minutes on consent for treatment. Assess and treat with manual therapy for the PFM, pelvic and abdominal muscles if indicated. Frequency – The treatment is scheduled for every two weeks unless the participant has her menstrual cycle or due to personal issues. The appointment was then rescheduled for the week after. The HEP are stretches for the pelvic musculature as per presentation of CPP pain patterns. The patient is advised the application of cryotherapy for 15 minutes if she was sore after treatment.
complete the final questionnaires and discharge from the trial but care continues.	

Table 3.1: Procedure, treatment and frequency for group A

Clinical Research Ethics Committee of the Cork Teaching Hospitals.

Procedure	Treatment and Frequency
Group B:	
 1st treatment – Trial check list to be completed by the physiotherapist. Consent forms to be filled by the participants. Complete three baseline questionnaires (NPRS, FSFI, IPPQ). Subjective and objective assessment along with education of pelvic muscle involvement and treatment entailed. Education on good bladder, bowel and dietary habits if indicated. Signing of consent forms for treatment, TrDN 	Initial assessment of posture, spine and PFM. Treatment is for 30-45 on consent for treatment. Only introduce TrDN if the participant is happy to start treatment. 2nd treatment - To perform superficial TrDN technique for the PFM as an introduction to the deep needling technique if the patient is apprehensive about TrDN followed by compression and stretching of the PFM. If the participant is particularly nervous, start with needling muscles

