and trial. Assess and treat with TrDN, TPR and distention for the PFM, pelvic and abdominal	 that are segmentally-related to the PFM such as the piriformis, rectus abdominous, gluteus and adductors. For trans-perineal TrDN for the PFM, start with needling the Levator-ani muscles followed by the required deep PFM and then if required needle the superficial PFM. The patient is advised application of cryotherapy for 15 minutes if sore after treatment. Frequency- Identical to group A.
 muscles per presentation. 4th treatment – complete NPRS 8th treatment-complete NPRS 	
 10th treatment or final treatment- due to positive outcomes, complete four final questionnaires (NPRS, FSFI, IPPQ, PTSS). 10th treatments – if no resolution is achieved, complete the final questionnaires and discharge from the trial but care continues. 	

Table 3.2: Procedure, treatment and frequency for group B

Clinical Research Ethics Committee of the Cork Teaching Hospitals.

Statistical analysis and power calculation

Since this is the first study to analyse TrDN for the PFM, the power in these studies (12,13,25) were compared and it was estimated that in order to determine a p<0.05, with 80% power, α =0.05, β =0.2, SD=1 for the outcome in the population and an effect size of 0.634, a total of 80 participants will be required. One hundred and twenty four participants will be invited as a participation rate of 70% is expected. Since studies analysing manual interventions for pelvic floor pain were not statistically significant (12,13), MCID was considered to be of practical significance. In chronic pain management, a 50% decrease in pain from baseline is rated as significant improvement, while a 30% decrease is rated as a meaningful improvement (38). Statistical analysis will be carried out using the IBM corp. SPSS software 24. Visual inspection of Histograms and Q-Q plots will be utilised to check the distribution of variables. A General Linear Model will be used to determine if the groups differed with regard to mean pain level at the endpoint of the study with pre-treatment score as the covariate in the analysis. The Kaplan Meier, non-parametric tests and Related Sample Wilcoxon Signed rank test are to be used for between-groups and within-group analysis.

Data monitoring

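### Table 3.1 asks Group A for the final questionnaires at the 8th treatment, against the Method section and Table 3.2, and no rule covers the additional set

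*Combined protocol and SAP*

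**What the plan says.** The questionnaire schedule appears in three places.

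- **Method section, both arms.** For pain: "NPRS will be given at baseline, the fourth, the eighth and the tenth treatment or earlier if resolution of symptoms occurred". FSFI and IPPQ are collected before treatment and at the last session; PTSS is collected at the last treatment only.
- **Table 3.2, Group B.** At the 8th treatment: "8th treatment-complete NPRS". The full set follows later: "10th treatment or final treatment- due to positive outcomes, complete four final questionnaires (NPRS, FSFI, IPPQ, PTSS" (closing bracket omitted), and for the others "10th treatments – if no resolution is achieved, complete the final questionnaires and discharge from the trial but care continues". This agrees with the Method section.
- **Table 3.1, Group A.** "8th treatment or when ceasing treatments due to positive outcomes – to complete four final questionnaires (NPRS, FSFI, IPPQ, PTSS" (closing bracket omitted). A further row, for women unresolved at the 10th treatment, says to "complete the final questionnaires and discharge from the trial but care continues".

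On analysis, the Method section describes a comparison before and after treatment, by intention to treat. The statistical section names a model for mean pain and lists some tests. It does not mention FSFI, IPPQ or PTSS, and it has no rule for a woman with two post-treatment sets.

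**The concern.** Only Table 3.1 departs from the common schedule, and it covers only one arm. The arms are also delivered by different people at the maternity hospital: three physiotherapists share Group A, and the researcher alone treats Group B. Staff who follow their own arm's table could collect the same questionnaires at different times in the two arms.

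FSFI and IPPQ carry the stated secondary objective, and PTSS carries treatment satisfaction. If Group A has an additional, earlier set, someone must choose which set to analyse. Without a written rule, that choice could be made after the results are known. It could also leave Group A with post-treatment data for women whose Group B counterparts have none.

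**Working it through.** The plan states no figure on this point, so the check sets the instructions side by side and counts forms.

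**Inputs**
- Form timing: Tables 3.1 and 3.2 and the Method section, as above.
- Visit interval: "The treatment is scheduled for every two weeks unless the participant has her menstrual cycle" or has personal reasons; "The appointment was then rescheduled for the week after". Table 3.2 gives Group B the same frequency.
- Forms are filled in before the session (Data monitoring).

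**Step 1. NPRS.** For a woman who reaches the 10th treatment unresolved, NPRS is due at treatments 1, 4, 8 and 10 in both arms. There is no conflict.

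**Step 2. Post-treatment FSFI, IPPQ and PTSS sets per woman.** The literal reading takes the 8th treatment in Table 3.1 as a fixed collection point. The narrow reading confines that row to women who stop for a good outcome, at whatever session.

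| Woman's course | Group A, literal | Group A, narrow | Group B |
|---|---|---|---|
| Good outcome, stops at or before the 8th | 1 | 1 | 1 |
| Unresolved, reaches the 10th | 2 | 1 | 1 |
| Leaves unresolved after the 8th, before the 10th | 1 | 0 | 0 |
| Good outcome at the 9th or 10th | 1 or 2 | 1 | 1 |

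The 1 or 2 in the last row depends on the word joining the two conditions in Table 3.1. If it means either one, she has a single set, from the 8th, which was not her last treatment. If it means both, she has two.

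**Step 3. Distance between the two forms, if Group A's 8th were set against Group B's 10th.**
- Sessions already received: 8 − 1 = 7 and 10 − 1 = 9, a difference of 2 treatments. The difference is the same if forms are filled in after the session (8 and 10).
- Fortnightly visits: 7 × 2 = week 14 and 9 × 2 = week 18, a gap of 4 weeks.
- Every visit put back a week: 7 × 3 = week 21 and 9 × 3 = week 27, a gap of 6 weeks.

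**Step 4. Effect on scores.** This cannot be derived. The documents give no time course and no standard deviation for FSFI, IPPQ or PTSS in this population.

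**Step 5. Are the forms likely to exist already?** Recruitment ended in November 2017. Assume the last woman had her first treatment on 30 November 2017. Her 10th falls 18 weeks later, on 5 April 2018, or 27 weeks later, on 7 June 2018, if every visit slipped a week. These dates are 145 and 82 days before this version (28 August 2018). A waiting-list delay of more than about 21 weeks (145/7) or 12 weeks (82/7) would put her last form after it.

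**The case against.** The strongest reply is that a harmless reading exists. The clause on stopping for a good outcome has no session limit. A Group A woman who stops well at the 9th or 10th can complete the set then, as in Group B, and the 10th-treatment row covers the rest. On that reading each such woman has one set and the arms do not differ. This stands, and it rules out the claim that the arms are out of step on every reading, or that Group A's last good-outcome form always follows 7 sessions against 9 in Group B. It does not clear the row, which names the 8th treatment without confining it to women who stop then.

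Second, the plan is not silent on which form counts. The Method section ties FSFI and IPPQ to the last session and PTSS to the last treatment, and it describes a before-and-after comparison. That points to the last-session form, and with it the shift is zero for women who have that form. What is missing is narrower: a rule for an additional 8th-treatment set.

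Third, final forms fall at different session numbers by design, because treatment stops at resolution. That is also true, and no change to Table 3.1 removes it. The point is only that the same rule should apply in both arms.

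A reader might also infer that the primary objective or the pain model is compromised, since the model's endpoint is not tied to a session. The documents do not support that link. The model concerns pain, and Table 3.1 leaves the NPRS schedule unchanged.

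**Conclusion.** The inconsistency is real and minor. Table 3.1 conflicts with the Method section and Table 3.2 on when Group A completes FSFI, IPPQ and PTSS.

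Its size depends on how the row was applied. Taken literally, it yields two sets against one for unresolved women who reach the 10th treatment, and one against none for women who leave unresolved between the 8th and 10th. It also permits a comparison two treatments apart (4 weeks at fortnightly visits, 6 if every visit slips). Taken narrowly, it need have no effect.

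A reader might infer a demonstrated bias between the arms. The documents do not show one: the score shift cannot be calculated and may be zero. NPRS timing, the pain model and the number-of-treatments objective are unaffected.

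**What to change.** 1. Reconcile Table 3.1 with the Method section and Table 3.2, so that both arms complete NPRS at the 8th treatment, and FSFI, IPPQ, PTSS and NPRS at the last treatment. If forms were already collected under Table 3.1, keep that record and note it; do not rewrite it.
2. Add one analysis rule for both arms: the FSFI, IPPQ and PTSS form analysed is the one from the woman's last treatment.
3. Report by arm the number of women who have such a form.
4. Where a woman's only post-treatment set is from the 8th treatment and that was not her last, treat the last-treatment form as missing in the main comparison, and include the 8th-treatment form in a sensitivity analysis.

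The cost is one table row (or a note of what was collected), a short analysis rule and one count by arm. Because most forms may already exist, the analysis rule does most of the work. The downside is that some Group A 8th-treatment forms stay out of the main comparison, and a few women may have no last-treatment form there, which matters under intention to treat. The count and the sensitivity analysis make that loss visible.

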In a meta-analysis (23), the study that included TrDN with stretches showed a significant increase in the ROM of the muscles (p=0.043) compared to stretches alone. The treatment duration was three weeks.

An RCT (25) that reviewed stretches combined with TrDN for chronic non-specific neck pain found 58% (n=65) in the combined intervention group required only two treatments from the allocated four to report resolution of symptoms.

A study (26) on temporomandibular dysfunction (TMD) found that the deep TrDN technique for MTrPs (n=36) had a lasting effect for up to six months post-treatment and showed a significant improvement in pain and increased ROM of the jaw after just one treatment for three weeks (p<0.01).

Research Hypotheses

Null hypothesis: The inclusion of trans-perineal TrDN to manual therapy will not influence the number of treatments required to achieve a clinically meaningful reduction in pain within the allocated ten sessions. It will not affect the outcomes for the pain variables and dyspareunia across the categories of treatments.

Research hypothesis: The inclusion of trans-perineal TrDN to manual therapy will influence the number of treatments required to achieve a clinically meaningful reduction in pain within the allocated ten sessions along with a variation in outcomes across the variables evaluated.

Method

This open label non-randomised clinical trial will compare two interventions pre-and posttreatment. This trial will be analysed by intention to treat. The ethical approval was obtained from the Clinical Research Ethics Committee of the Cork Teaching Hospitals in March 2016.

The trial is conducted at the Cork University Maternity Hospital (CUMH) and the Cork Women's Clinic (CWC). CUMH is a large Obstetrics and Gynaecology hospital governed by the Health Service Executive. CWC is a private gynaecology clinic. Female participants will be referred for physiotherapy as deemed appropriate by the inclusion and exclusion criteria (Table 1) given to the gynaecology team at CUMH and CWC.

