- Neurological conditions such as stroke, epilepsy, Parkinson's disease etc.
- Fibromyalgia and chronic fatigue syndrome.
- Undergoing any treatment such as Botox or analgesic injections which can interfere with physiotherapy outcomes.

Exclusion criteria for dry needling

- Extreme needle phobia, rheumatoid arthritis, prolonged corticosteroid treatment, warfarin treatment, heart implants and blood clotting disorders.
- Participant should have no significant learning disability and should be able to understand the procedure to consent for a vaginal examination and for treatment.
- Participant should not require a chaperone during treatment in order to avoid administrative issues.

Clinical Research Ethics Committee of the Cork Teaching Hospitals.

Recruitment and allocation

Women will be invited for the trial with a letter of invitation. On confirmation of interest in the trial, their medical record numbers and names will be documented onto an excel sheet with the month of referral. In order to accommodate for the CUMH physiotherapy waiting list and to allow for the clinical workings at CUMH, an excel sheet with six names will be emailed to the central appointments office at CUMH. Two CUMH secretaries unrelated to the trial will randomly allocate the names into two opaque envelopes marked as group A and group B.

The staff will allocate appointments for group A among three Chartered Physiotherapists in Women's Health and Continence involved in the trial, including the researcher. The participating physiotherapists will have no input in the allocation process and they all have clinical experience of over 15 years.

Group B will be treated only by the researcher who has a clinical experience of eight years using trans-perineal TrDN. An identical procedure will be piloted at the CWC. The researcher will provide the treatment for both groups at the CWC. The participant's file will be marked as Group A or B to inform about allocation. The recruitment process will ran from April 2016 to November 2017.

Withdrawal from participation

An individual can decline participation in the trial at any stage of the trial. If a participant reports needle phobia after group allocation, she will be transferred to group A. If a participant refuses dry needling treatment after starting the treatment in group B, she will be removed from the trial but care will continue.

Interventions

Group A: Manual therapy

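### The arm tables ask for final questionnaires before the late sessions only after a positive outcome; this conflicts with the Method section, differs by arm, and puts the endpoint data of early stoppers without benefit at risk

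*Combined protocol and SAP*

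**What the plan says.** - **Table 3.1 (group A).** NPRS is taken at the 4th treatment. The four final questionnaires are due at "8th treatment or when ceasing treatments due to positive outcomes". Women without resolution complete the final set at the 10th treatment ("10th treatments – if no resolution is achieved").
- **Table 3.2 (group B).** NPRS alone is taken at the 4th and 8th treatments. The final set follows this line: "10th treatment or final treatment- due to positive outcomes, complete four final questionnaires". Women without resolution complete it at the 10th treatment.
- **Method.** NPRS is due at baseline, at the 4th and 8th treatments, and at the "tenth treatment or earlier if resolution of symptoms occurred without the requirement of the allocated ten treatments". FSFI and IPPQ are due before treatment and at the last session, and PTSS at the last treatment, none of them conditional on response. The section also states: "This trial will be analysed by intention to treat".
- **Withdrawal from participation.** "An individual can decline participation in the trial at any stage of the trial". The section does not say what is collected from a woman who leaves. A group B woman who refuses needling after starting is taken out of the trial.
- **Statistical analysis and power calculation.** The plan names a General Linear Model for endpoint pain adjusted for baseline, Kaplan-Meier, non-parametric tests and the related-samples Wilcoxon test. It gives no missing-data method, no censoring rule and no drop-out rate.
- **Data monitoring.** Questionnaires may be completed at home.

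**The concern.** If the tables are followed literally, whether an endpoint is observed can depend on its value. A woman who stops at session 5 because she is better is asked for all four instruments. A woman who stops at session 5 because she is no better is asked for none.

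Final pain, FSFI, IPPQ and PTSS would then lean towards benefit in each arm, which matters for the planned within-group tests. If such stopping is unequal between arms, the comparison is biased too. Unequal loss is plausible: the trial is open-label, one arm adds a needling technique, and the removal rule for needling refusal applies to group B only. PTSS has no baseline, so it would describe mainly improvers and women who persisted. Kaplan-Meier, left to its default, censors early stoppers as if they would go on to improve at the rate of those who stayed. An intention-to-treat analysis needs a plan for these women, and none is given.

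**Working it through.** **1. The passages side by side.** What each asks of a woman after baseline:

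| Situation | Table 3.1 (A) | Table 3.2 (B) | Method |
|---|---|---|---|
| Stops before session 4, no benefit | nothing | nothing | no NPRS; FSFI, IPPQ, PTSS at last session |
| Stops from session 4 to 7, no benefit | NPRS at 4 | NPRS at 4 | NPRS at 4; FSFI, IPPQ, PTSS at last session |
| Stops at session 8 or 9, no benefit | NPRS at 4; all four at 8 | NPRS at 4 and 8 | NPRS at 4 and 8; FSFI, IPPQ, PTSS at last session |
| Stops before session 10 because of a positive outcome | all four | all four | all four |
| Reaches session 10 without resolution | all four | all four | all four |

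The first three rows show the conflict between the tables and the Method section. The third also shows the difference between arms: group A gives a full set at session 8 and group B only NPRS.

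**2. Yardstick from the plan.** The inputs are an effect size of 0.634, SD 1, α = 0.05 and 80% power (Statistical analysis and power calculation); a two-sided test and 1:1 allocation are assumed. Per arm, n = 2 × (1.960 + 0.842)² / 0.634² = 2 × 7.85 / 0.402 = 39.05, rounded up to 40. The total of 80 is reproduced. Bias can be judged against 0.634 SD.

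**3. Proportion improved.** All loss rates from here on are assumptions, because the documents give none. Let true improvement be 50% in both arms and let only non-improvers leave, which is the extreme case. The observed proportion is 0.5 / (1 − d).

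| Loss d | 5% | 10% | 20% | 30% |
|---|---|---|---|---|
| Observed improved | 52.6% | 55.6% | 62.5% | 71.4% |

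The false difference is 2.9 points at 10% against 5%, 9.9 points at 20% against 5%, and 15.9 points at 30% against 10%. It favours whichever arm loses more.

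**4. Mean final pain.** Let improvers end at NPRS 2 and non-improvers at 6, so the true mean is 4.0. The observed mean is [0.5 × 2 + (0.5 − d) × 6] / (1 − d). At 20% it is 2.8 / 0.80 = 3.50; at 5% it is 3.7 / 0.95 = 3.89.

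**5. A milder loss model in SD units.** Let those lost be drawn at random from the worse half of their own arm. The mean of the worse half of a normal distribution lies 0.798 SD below the arm mean, so completers shift by 0.798 × d / (1 − d): 0.09 SD at 10% and 0.20 SD at 20%.
- Equal loss leaves the between-arm difference about unchanged, but each arm's improvement is still inflated.
- 10% in A and 20% in B adds 0.11 SD in favour of B (0.11 / 0.634 = 17% of the design effect). Swapping the arms subtracts the same amount.
- 0% in A and 20% in B adds 0.20 SD (0.20 / 0.634 = 32%).

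**6. Kaplan-Meier.** Take 40 women with 10, 6 and 4 improving at sessions 4, 8 and 10.
- No loss: 1 − (30/40)(24/30)(20/24) = 50%.
- 8 non-improvers censored after session 4: 1 − (30/40)(16/22)(12/16) = 59.1%.
- 4 or 2 censored: 53.8% or 51.8%.

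**7. Counting early stoppers as not improved.** If loss occurs before improvement and is unrelated to outcome, 20% against 5% gives 0.5 × 0.80 = 40% and 0.5 × 0.95 = 47.5%. This is a false gap of 7.5 points, so the rule can itself bias the comparison.

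**The case against.** The strongest reply is that the Method section already requires FSFI, IPPQ and PTSS at the last session whatever the response. That covers an agreed stop without benefit, and the tables may be loosely worded rather than restrictive. This stands in part. It shows that the passages need reconciling, not that the tables prevail. It does not cover a woman who simply stops attending, since nobody knows in advance which session is her last, and it does not extend to the unscheduled NPRS.

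Three stronger readings are tempting, and the documents do not support them.
- A reader might infer that in both arms only a positive outcome or the 10th treatment triggers the final set. In group A the 8th treatment is a separate trigger that does not depend on response.
- A reader might infer that early stoppers give no endpoint data at all. NPRS is scheduled at sessions 4 and 8 in both arms whatever the response. Only a woman who stops before session 4 has no pain score after baseline, and later stoppers can enter Kaplan-Meier as censored.
- A reader might infer that the outcomes are in fact selected on response. The withdrawal section is silent on exit data; it does not say that none is collected. A woman who feels better and stops attending may be missed too. Selection is a risk, not an established fact.

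It is also fair to say that the illustrations rest on invented rates, and that those in which only non-improvers leave are an extreme case.

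**Conclusion.** The point holds as a risk created by conflicting and incomplete instructions. Under the tables, a woman who stops without benefit before the 8th treatment (A) or the 10th (B) is not asked for the final set. She may leave no final FSFI, IPPQ or PTSS and no NPRS after the last scheduled one. The Method section conflicts with the tables on this, the timing differs by arm, and the stated intention-to-treat analysis has no missing-data or censoring rule behind it.

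The expected bias is towards benefit within each arm. Between arms it arises only if such stopping is unequal, and it can go either way. Its size cannot be known from the documents. Under the milder assumed model, a gap of 10 percentage points in loss (10% against 20%) moves the difference by about 0.11 SD, against a design effect of 0.634. The point should be addressed, but it does not by itself invalidate the trial.

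**What to change.** - **One collection rule.** Reconcile the Method section and Tables 3.1 and 3.2 so that, in both arms, the four final questionnaires are completed when trial treatment ends for any reason, or at the 10th treatment. Send them home if a woman stops attending; Data monitoring already allows home completion.
- **Withdrawal from participation.** Separate stopping treatment, after which questionnaires are still requested unless she declines, from withdrawing consent for data. Record the reason for stopping.
- **Analysis and reporting.** Use the session 4 and 8 NPRS for early stoppers, report early stopping by arm and reason, and state the Kaplan-Meier censoring rule. Count early stoppers as not improved in a sensitivity analysis only, since step 7 of the working shows that this rule can create its own difference.

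**Cost.** The change is a wording revision and some posted forms, with no new instrument, visit or staff. Some forms will not come back, so a missing-data statement is still needed.

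**Timing.** This version is dated August 2018 and recruitment is given as ending in November 2017. Ten fortnightly sessions span nominally (10 − 1) × 2 = 18 weeks, before any waiting list or rescheduling. If data collection has already ended, only the analysis and reporting parts still apply, together with whatever reasons for stopping can be recovered from existing records.

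### The stated 80% power with 80 participants fits a comparison of two fully observed means and is not established for the primary outcome, the number of treatments to improvement within ten sessions

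*Combined protocol and SAP*

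**What the plan says.** All references are to the combined protocol and SAP.

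- **Primary objective (Method):** "The primary objective is to evaluate the number of treatments required within the allocated ten treatments to effect improvement in pain in both groups". The null hypothesis (Research Hypotheses) is that adding needling "will not influence the number of treatments required to achieve a clinically meaningful reduction in pain within the allocated ten sessions".
- **Sample size (Statistical analysis and power calculation):** "SD=1 for the outcome in the population and an effect size of 0.634, a total of 80 participants will be required", with 80% power and alpha 0.05, after comparing three cited studies. No outcome, test, sidedness or allocation ratio is given.
- **Analyses (same section):** "A General Linear Model will be used to determine if the groups differed with regard to mean pain level at the endpoint", with the pre-treatment score as covariate. Then: "The Kaplan Meier, non-parametric tests and Related Sample Wilcoxon Signed rank test are to be used for between-groups and within-group analysis". No method is assigned to the number of treatments.
- **Improvement (same section):** "a 50% decrease in pain from baseline is rated as significant improvement, while a 30% decrease is rated as a meaningful improvement". Neither percentage is tied to the primary outcome.
- **Measurement (Method):** "NPRS will be given at baseline, the fourth, the eighth and the tenth treatment or earlier if resolution of symptoms occurred".
- **End of follow-up (Tables 3.1 and 3.2), at the tenth treatment:** "if no resolution is achieved, complete the final questionnaires and discharge from the trial but care continues".

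**The concern.** A standardised difference with SD 1 describes two sets of fully observed values. The number of treatments is not fully observed. A woman who has not reached the defined reduction by session ten leaves the trial, and her count is known only to exceed ten. A woman who improves without full resolution is recorded as improved only when the pain scale is next given, so her count is known only to an interval. The calculation has no input for the proportion improving, for censoring or for the assessment schedule.

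What is at stake is how a null result would be read. If no difference in number of treatments is found, a reader who takes the 80% at face value could treat it as well-powered evidence that needling does not speed improvement.

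**Working it through.** **1. Reproduce N = 80.** From the plan: effect 0.634, SD 1, alpha 0.05, power 80%. Assumed: two-sided test, 1:1 allocation.

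- Normal formula: n per arm = 2 × (1.960 + 0.842)² / 0.634² = 2 × 7.849 / 0.402 = 39.05, rounded up to 40, so 80 in total.
- Two-sample t-test: 40.04 per arm; power at 40 per arm is 79.96%.
- One-sided, normal formula: 31 per arm, 62 in total, which does not match.
- Reading 0.634 as a log hazard ratio (hazard ratio 1.89): events = 4 × 7.849 / 0.402 = 78.1, so 79. Nearly all 80 women would have to improve, and the stated SD of 1 points to means.

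That the figure is a comparison of means is an inference from this match.

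**2. Compare with the primary outcome.** The only comparison of means named in the power paragraph is the General Linear Model on endpoint pain, which is not the primary outcome. If the unnamed outcome is instead the session count, the calculation still treats every count as fully observed.

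**3. Illustrate the size.** None of the following is in the documents. Assume a normal session count (SD 1.5, 2.5 or 4), rounded to whole sessions with a floor of 1, Group B shifted by 0.634 SD, and 40 per arm. Women above ten are censored (log-rank) or tied above ten (Mann-Whitney). Simulated power, dated at every session:

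| Group A improving by session ten | Mean events | Log-rank | Mann-Whitney |
|---|---|---|---|
| 35% | 38 | 0.67–0.68 | 0.69 |
| 59% | 56 | 0.72–0.73 | 0.75 |
| 75% | 66 | 0.73–0.75 | 0.76–0.77 |
| 90% | 75 | 0.72–0.75 | 0.76–0.77 |

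- Dated only at sessions 4, 8 and 10: log-rank 0.66–0.71, Mann-Whitney 0.65–0.73.
- Same shift with no cap, dated at every session: log-rank 0.72–0.75, Mann-Whitney 0.76–0.78.
- Simulation error is about one point, so the ranges are quoted as about 65–73% (scheduled dating) and 67–78% (every session).

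At 59% improving, the log-rank test loses about 5 points from the change of test and 1–2 from the cap. The cap matters most when few improve (7–9 points at 35%).

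**4. Effect detectable with 80 women.** Under proportional hazards, pB = 1 − (1 − pA)^HR, events D = 40 × (pA + pB), and D × (ln HR)² / 4 = 7.849.

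- pA = 0.59, the rate that the literature review cites for a ten-treatment manual-therapy arm: HR = 2.09, pB = 0.85, D = 57.4. Simulated log-rank power at HR 2.10 is 0.803 with dating at every session and 0.790 with dating at sessions 4, 8 and 10.
- All 80 reach the event: HR = exp(2.8016 / √20) = 1.87. Simulated power is 0.773 at 1.87 and 0.793 at 1.90.
- Power can be far lower or higher. At HR 1.5 it is 44% even with 80 events. For 35% against 81% resolving (the injection study in the literature review), HR = ln 0.19 / ln 0.65 = 3.86 with 40 × (0.35 + 0.81) = 46.4 events, and power exceeds 99%.

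**5. What a null result would leave open.** With 59% improving in both arms, events = 80 × 0.59 = 47.2 and SE of the log hazard ratio = 2 / √47.2 = 0.291. An observed hazard ratio of 1 has a 95% CI of exp(±1.96 × 0.291) = 0.57 to 1.77.

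**The case against.** The strongest reply has five parts.

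- **The sponsor's arithmetic is right.** This stands. The defect is an unnamed outcome and test.
- **The outcome behind SD 1 may be the session count.** The literature review describes one of the three source studies by how many of its allocated treatments were needed. This cannot be excluded, so the documents do not show that the figure was built on endpoint pain. It does not rescue the 80%, because a comparison of fully observed means ignores the cap and the assessment schedule.
- **The simulated shortfall is hypothetical.** This stands too. The shift model, the normal shape and the SDs are assumptions, and at 59% improving most of the log-rank loss comes from the choice of test. The 59% itself is marked improvement in painful bladder syndrome, not a 30% or 50% fall in the pain score. The range illustrates and does not estimate this trial's power.
- **More than 80 women may enrol.** 124 × 0.70 = 86.8, about 43 per arm. The same model, dated at every session, then gives log-rank 0.75–0.76 and Mann-Whitney 0.77–0.79 at 59% improving, and 0.71–0.73 across the two tests at 35%. This narrows the gap, before any dropout.
- **The plan nowhere says it will read a null result as no benefit, and the interval in step 5 excludes a hazard ratio of 2.1.** Both are true. The risk lies in how the 80% may be cited, and effects up to 1.77 would remain open.

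A reader might infer that the trial is underpowered. The documents do not support that, because they give no event rate or hazard ratio, and large effects have 80% power or more. A reader might also infer that every woman without resolution at session ten is censored. Only those who have not reached the defined reduction are.

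**Conclusion.** The concern holds in limited form. The 80% reproduces only as a two-sided, 1:1 comparison of two fully observed means, and nothing in the plan carries it over to the number of treatments. Under the assumed 0.634 SD shift in session count, with 35% to 90% of Group A improving and no dropout, the shortfall at 40 per arm is modest: about 65–73% with scheduled dating, or 67–78% with dating at every session. The finding is a mismatch between the stated power and the primary outcome. It is neither a calculation error nor proof that 80 women are too few. Confidence is medium, because the outcome behind 0.634 is not stated.

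**What to change.** No extra enrolment is needed.

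1. State which outcome and test the 0.634 SD figure was calculated for, and do not present 80% as the power for number of treatments.
2. Assign one of the between-group methods already planned to the primary outcome: the log-rank test with the Kaplan-Meier analysis, or a rank test with non-improvers ranked above ten. State which of the two percentages defines the event. Date each event at the pain-scale session where the reduction is first recorded, with a method that allows for ties or interval dating. Treat as censored at ten only women who have not reached it. Report the effect with a 95% CI.
3. Restate the detectable effect for that test under declared assumptions. For the log-rank test, for example: if 59% of Group A improve within ten treatments (assumed from a cited manual-therapy arm), 80 participants give about 80% power for a hazard ratio of about 2.1; this was worked out after recruitment closed and is not the basis for the sample size.

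Recruitment and allocation gives November 2017 as the end of recruitment and this version is dated August 2018, so the label is needed. The cost is a rewritten paragraph and one named test. The power stated for the primary outcome becomes less favourable, and the restatement is visibly retrospective.
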